#### 6.4 Secondary endpoint

#### 6.4.1 Safety

Expected adverse event (AE) related to BTXA injection of the puborectalis include:

- Bruising at injection site
- Local skin reaction at injection site
- Pain at injection site
- Infection at injection site
- New or worsening faecal incontinence

Following the injection, any adverse event reported by the patients will be recorded on the adverse event (AE) form on the patient's eCRF using Research Electronic Data Capture (REDCap). This form will record the nature, severity, time of onset of, and treatment required for the AE. Patients are encouraged to self-report any adverse events as soon as possible by telephone. If no adverse events have been self-reported this will be confirmed with the patient at the end of every follow-up appointment as part of the follow-up procedure. In addition, at the time of first follow-up the injection site will be inspected for any signs of bruising, local skin reaction, or infection. At each follow-up, St. Mark's incontinence score will also be measured to allow detection of new or worsening incontinence, which is the main procedure specific risk associated with this procedure.

The severity of any adverse events will be classified according to the Clavien-Dindo classification of surgical complications:

- Grade 1 any deviation from normal post-operative course without need for pharmacological (antiemetics, antipyretics, analgesics, diuretics, and electrolytes are permitted), surgical, endoscopy, or radiological interventions
- Grade 2 requiring pharmacological treatment other than those permitted in 1 (including blood transfusion and total parenteral nutrition)
- Grade 3 requiring surgical, endoscopic, or radiological intervention
  - Grade 3a not under general anaesthetic
  - Grade 3b under general anaesthetic
- Grade 4 life-threatening complication requiring intensive care management
  - Grade 4a single organ dysfunction, including dialysis
  - Grade 4b multi-organ dysfunction
- Grade 5 death

Serious adverse events (SAE) will be recorded as above and will also be reported as described in the safety reporting section (see Section 16).

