#### Visit 3: BTXA injection

The BTXA injection will be scheduled by the radiology department within 12 weeks. The patient and radiologist carrying out the injection will complete a procedurerelated questionnaire after the procedure. Ultrasound and EMG report on each patient will be obtained following the procedure. The patient will be asked to report any adverse events following the BTXA injection as soon as possible by phone or at follow-up.

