#### Visit 4: first follow-up

The patient will attend first follow-up 4-6 weeks after the injection and complete the Cleveland Clinic constipation scoring (CCCS) as well as St. Mark's incontinence scoring (SMIS). They also undergo a repeat anorectal physiology tests.

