#### Visit 5: second follow-up

The patient will be given the option of telephone, face-to-face, or electronic follow-up at 3 months following the injection and will complete the CCCS and SMIS. They will also be asked if they have experienced any adverse events.

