At any stage of the study, expected adverse events will be recorded on the patient's eCRF. If no adverse events have been self-reported this will be confirmed with the patient at the end of every follow-up appointment as part of the follow-up procedure. Serious or unexpected adverse events will be recorded and also reported according to research governance framework guidelines (see Section 14).

Patients can withdraw at any point in the study without the requirement to provide a reason. The data collected from the point of consent to the point of withdrawal will be kept for analysis of retention and follow-up rate, as well as incidents of adverse events depending on the stage at withdrawal. Such patients will return to routine care.

					-~~{	Lon				

Figure 3a. EMG of puborectalis demonstrating tonic activity at rest

Figure 3b. EMG of puborectalis demonstrating voluntary contraction

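### The first injection-site inspection and the first staff question about adverse events both come 4–6 weeks after injection, so minor local reactions that have already resolved may be missed or poorly dated and graded.

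*Combined protocol and SAP*

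**What the plan says.** Section 6.4.1 opens its list with "Expected adverse event (AE) related to BTXA injection of the puborectalis include" and names five events: bruising, local skin reaction, pain and infection, all at the injection site, and faecal incontinence that is new or has worsened. Capture runs through four routes.

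- **Patient-initiated report.** Section 6.4.1: "Patients are encouraged to self-report any adverse events as soon as possible by telephone". The Visit 3 text in Section 9: "The patient will be asked to report any adverse events following the BTXA injection as soon as possible by phone or at follow-up".
- **Staff prompt.** Section 6.4.1: "If no adverse events have been self-reported this will be confirmed with the patient at the end of every follow-up appointment". Section 9 repeats the rule after describing the intervention: "this will be confirmed with the patient at the end of every follow-up appointment as part of the follow-up procedure".
- **Inspection.** Added to the two routes above: "at the time of first follow-up the injection site will be inspected for any signs of bruising, local skin reaction, or infection".
- **A scored instrument**, for incontinence only: the St. Mark's score at each follow-up.

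On timing, the Visit 4 text says: "The patient will attend first follow-up 4-6 weeks after the injection". For visit 5, "The patient will be given the option of telephone, face-to-face, or electronic follow-up at 3 months", and visit 6 is described as similar. No inspection is planned at either, so the visit 4 inspection is the only one. The Visit 4 text itself mentions neither the inspection nor the adverse-event check. Both rest on the general statements in Sections 6.4.1 and 9.

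**The concern.** Bruising and minor skin reactions are usually thought of as early and short-lived. An examination a month or more after the needle is poorly placed to see them, and the staff prompt comes at the same visit. Nothing scheduled falls in the period when such events are most likely to be present.

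Safety is the first secondary objective in Section 6.2. Section 5.1 presents the clean field, and the lower infection risk expected from it, as an advantage of the new route. Section 5.2 says that identifying the muscle by this route has not been described in adults, so these 10 patients will supply the local-reaction data carried into a later trial. Missed events can only lower the recorded rate, which is the direction that favours the technique.

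**Working it through.** **Step 1. Timing of the inspection.** The visit table in Section 9 puts the injection at week 18 and first follow-up at weeks 22–24. 22 − 18 = 4 and 24 − 18 = 6 weeks, or 4 × 7 = 28 to 6 × 7 = 42 days. This reproduces the 4–6 weeks in the Visit 4 text. Scheduled contacts between visit 3 and visit 4: none.

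**Step 2. Capture route for each expected event.**

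| Expected event | Before day 28 | At visit 4 (day 28–42) |
|---|---|---|
| Bruising | Patient telephones | General prompt + inspection |
| Skin reaction | Patient telephones | General prompt + inspection |
| Infection | Patient telephones | General prompt + inspection |
| Pain at site | Patient telephones | General prompt |
| Incontinence | Patient telephones | General prompt + St. Mark's score |

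Inspection covers 3 of 5. All four injection-site events share the early gap. Pain is included because the questionnaire in Section 6.4.2 is completed at the end of the procedure and asks about pain during it, not afterwards. Events with no staff prompt at any time: 0 of 5.

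**Step 3. What the inspection can see.** A sign that starts on day *t* and lasts *d* days is still visible on day *v* only if *t* + *d* ≥ *v*. The documents give no value for *d*. Assume 1–3 weeks (7–21 days):

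- Onset at injection (*t* = 0): the sign has gone by day 21 at the latest, before the earliest inspection on day 28.
- With *d* = 21, it is visible only if *t* ≥ 28 − 21 = 7 for the earliest visit, or *t* ≥ 42 − 21 = 21 for the latest.
- With *d* = 7, the same limits are 28 − 7 = 21 and 42 − 7 = 35.

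A sign lasting 28 days or more would be seen at the earliest visit whatever its onset. The answer therefore depends on the assumed duration.

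**Step 4. What incomplete capture would do (illustration).** Let *p* be the true rate of an event and *s* the share recorded by any route. Both are assumed. The chance of recording at least one event in 10 patients is 1 − (1 − *ps*)^10.

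| *s* | *p* = 10% | *p* = 20% |
|---|---|---|
| 1.00 | 0.651 | 0.893 |
| 0.75 | 0.541 | 0.803 |
| 0.50 | 0.401 | 0.651 |
| 0.25 | 0.224 | 0.401 |

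If 0 of 10 are recorded, the exact two-sided 95% upper limit is 1 − 0.025^(1/10) = 30.8%. That limit applies to *ps*. For the true rate it becomes 30.8%/*s*: 30.8%/0.75 = 41.1%, or 30.8%/0.50 = 61.7%.

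**The case against.** A reader might infer that the three inspected events rest on unprompted self-report alone. The documents do not support this. The sentence just before the inspection provision has staff confirm with the patient at every follow-up when nothing has been reported. Section 9 repeats it, and the Visit 5 text asks about adverse events at 3 months. The inspection is an addition to these routes, and an event recalled at visit 4 counts whether or not it can still be seen.

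A reader might also infer that the inspection will find nothing. That follows only from an assumed duration shorter than 28 days. Likewise, nothing in the documents shows that patients seldom telephone, and at visit 3 they are specifically asked to.

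Other points weigh against the concern. An infection needing treatment is likely to be reported or remembered, and Section 5.3.2 puts infection and bleeding from injection below 1 in 10,000, or fewer than 10 × 1/10,000 = 0.001 expected cases here. The study is a descriptive convenience sample. Incontinence, which Section 6.4.1 names as the main procedure-specific risk, is measured with a score. Even with full capture, 0 of 10 leaves a limit of 30.8%.

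These arguments limit the size of the problem but do not remove it. The first prompt comes no earlier than the inspection. As described, it is general and framed as confirming that nothing was reported, with no item for each expected event. The layout of the REDCap form is not reproduced, so it may list the events, but the protocol does not say so. Sections 6.4.1 and 16 require severity and time of onset on the adverse-event form, and recall over 4–6 weeks is a weak source for both, above all for Clavien-Dindo Grade 1 events.

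**Conclusion.** The point holds as a gap in early, structured capture. The only site inspection and the first staff prompt fall 28–42 days after injection, with nothing scheduled before. It affects four of the five expected events, mainly the minor ones: bruising, skin reaction and post-procedure pain. Under-recording is plausible and would lower the local adverse-event rate. Its size cannot be computed from the documents, and the durations, event rates and capture shares used above are assumptions. The finding rests on two things: that some minor reactions resolve before day 28, and that a general question asked weeks later recovers fewer of them than an early question that names them. It does not touch the primary objective of technical feasibility. It is a worthwhile, inexpensive improvement to a secondary objective.

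**What to change.** - Add one short REDCap form or phone call about one week after injection, with yes/no items for the five expected events. The one-week timing is a judgement, chosen to fall well before day 28.
- At visit 4, ask about each of the five by name for the whole period since injection, and record onset and end dates. The form described in Sections 6.4.1 and 16 has time of onset but no end date.
- State the adverse-event questions and the inspection in the Visit 4 text, and keep the inspection as a check for persisting signs.

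The cost is one brief extra contact for each of 10 patients. REDCap is already in use, and telephone and electronic contact are already planned for visits 5 and 6, so no new staff or procedure is needed. The recorded rate of minor events may be higher as a result, and the report should say that they were actively sought.

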#### 6.4.2 Treatment acceptability

Treatment acceptability will be measured objectively by the recruitment rate and subjectively using a patient acceptability questionnaire, which will be completed by the participant at the end of the procedure. The questionnaire measures patient's overall opinion of the procedure, level of

pain during treatment, satisfaction with the duration of the procedure, and willingness to undergo the procedure again.

Question/Statement	Scoring
1. The procedure was painful.	□ Strongly agree □ Agree □ Neutral □ Disagree □ Strongly disagree
2. The procedure was embarrassing.	□ Strongly agree □ Agree □ Neutral □ Disagree □ Strongly disagree
3. The procedure was comfortable	□ Strongly agree □ Agree □ Neutral □ Disagree □ Strongly disagree

 
The procedure duration was too long.
 
	Strongly agree  Agree  Neutral  Disagree  Strongly disagree
5. What score corresponds best with your opinion of the treatment procedure? (10 = acceptable, 0 = unacceptable)	0 1 2 3 4 5 6 7 8 9 10 Unacceptable Neutral Acceptable
6. Reason for your answer in question 5.	(Free text)
7. Would you be willing to undergo this procedure again?	□ Yes □ No

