### 8. Study design

The overall design is of a single-centre, prospective, uncontrolled, open-label observational study. Patients diagnosed with dyssynergic defaecation, using Rome IV criteria, will be identified from weekly pelvic floor MDT and current waiting list for biofeedback therapy and invited to participate. BTXA injection is not offered as an alternative to biofeedback and does not preclude patients from receiving biofeedback therapy as per standard treatment as this is not a study of treatment efficacy.

All participants will undergo BTXA injection within 12 weeks of recruitment.

Data collection:

- Baseline data collection from patient's initial symptoms questionnaire and anorectal physiology report (pre-procedure).
- MYMOP questionnaire (pre-procedure and at final follow-up)
- Patient and physician procedural questionnaire to be completed at the end of the BTXA injection procedure (see Section 5.3 and 5.4).
- Cleveland clinic constipation score and St. Mark's incontinence score to be completed by the patient at each follow-up.
- Anorectal physiology report (post-procedure) for anorectal manometry results at first follow-up.
- Any adverse events reported by the patient will be recorded on an adverse event form (see Section 5.4).

Data analysis:

- Feasibility and efficacy outcomes will be extracted from the questionnaires and reports and recorded onto Research Electronic Data Capture (REDCap).
- Anonymised summary data will be exported to Excel and descriptive statistics (e.g. mean, confidence intervals of effect) used to present data for publication.

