### 9. Study procedures

#### **Recruitment**

Patients diagnosed with dyssynergic defaecation, using Rome IV criteria, will be identified from the weekly pelvic floor MDT and current waiting list for biofeedback therapy. These patients will be screened against the inclusion and exclusion criteria. Patients will be continually recruited until 10 patients have undergone the procedure, including re-recruitment for drop-outs.

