#### Visit 6: final follow-up

This will take place at 6 months following the injection and will be similar to the second follow-up but the patient will also be asked to complete a MYMOP follow-up questionnaire, and to rank their level of satisfaction with the treatment using a satisfaction thermometer.

Visit	Study Stage	Data		Week	Carried out by	Setting
0	Recruitment	N/A		0	Research team	Pelvic Floor MDT
1	Initial discussion	N/A		1-4	Clinical/research team	Phone
2	Consent and baseline data	CCCS SMIS Anorectal physiology MYMOP		5-6	Clinical/research team	Outpatient clinic
3	BTXA injection	Patient questionnaire Physician questionnaire	ting	18	Radiologist	Outpatient Ultrasound
4	First follow-up	CCCS SMIS Anorectal physiology	ts reporting	22-24	Clinical/research team	GI physiology
5	Second follow-up	CCCS SMIS	events	30	Clinical/research team	Outpatient clinic/ phone/ online form
6	Final follow-up	CCCS SMIS MYMOP follow-up Satisfaction thermometer	Adverse	42	Clinical/research team	Outpatient clinic/ phone/ online form

Study intervention (at visit 3):

Botulinum toxin type A injection (BTXA) – The intervention is an injection of 200 units of Botulinum toxin type A in to the puborectalis muscle under ultrasound guidance.

- In the prone position, the puborectalis muscle will be identified below the coccyx using ultrasound.
- After skin preparation using 70% Isopropyl Alcohol Pad, up to 5ml of local anaesthetic (1% lidocaine) an electromyography (EMG) needle will be inserted and the puborectalis muscle stimulated using a current to confirm correct needle position. Figure 3 demonstrates an example EMG trace on a healthy volunteer at rest (a) and under voluntary contraction (b)
- 200 units of BTXA (Botox, Allergan, Ireland) prepared in 2 ml of saline solution and drawn up using a 2ml syringe.
- 1ml (100 units) of BTXA solution is injected through the EMG needle into the puborectalis muscle to each side of the midline, achieving a total of 200 units.
- The needle is withdrawn, and the procedure is complete.

At the end of the procedure, the patient and physician both complete post-procedure questionnaires.

[figure not shown]

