# 12. Ethics

This study is a non-CTIMP study using BTXA injection, which is an established treatment for dyssynergic defaecation, and will adhere to the Research Governance Framework for Health & Social Care (2005), the World Medical Association Declaration of Helsinki (1996), ICH Good Clinical Practice Guidelines (1996), current applicable local regulatory requirements, and REC conditions of approval.

Patients with dyssynergic defaecation on the waiting list for biofeedback therapy are offered BTXA injection using a novel approach, avoiding the need for general anaesthetic. It is not offered as an alternative to biofeedback and does not preclude patients from receiving biofeedback therapy as per standard treatment, as the aim of the study is not to assess efficacy of this treatment in isolation but to ascertain its acceptability to patients and physician. The additional symptom questionnaire and anorectal physiology tests performed at follow-up will assess the need for further treatment, which may be biofeedback therapy or repeat injection with BTXA, as part of ongoing NHS care.

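### Does the undefined recruitment rate leave the acceptability outcome open to choice after the data are seen?

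*Combined protocol and SAP*

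**What the plan says.** Section 6.4.2 pairs one objective measure of acceptability with one subjective one: "Treatment acceptability will be measured objectively by the recruitment rate and subjectively using a patient acceptability questionnaire". The questionnaire is the one "which will be completed by the participant at the end of the procedure". Section 11.2 does not name the recruitment rate; it falls under the other outcomes to be summarised descriptively, without hypothesis testing.

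The word *recruitment* appears in several places:

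- The Section 9 visit table has a row "Recruitment N/A" at week 0, set at the pelvic floor MDT, followed by "Initial discussion N/A" at weeks 1-4. Consent is at weeks 5-6 and injection at week 18.
- Section 8: "All participants will undergo BTXA injection within 12 weeks of recruitment".
- Section 9, Recruitment: patients "will be identified from the weekly pelvic floor MDT and current waiting list for biofeedback therapy", and "Patients will be continually recruited until 10 patients have undergone the procedure, including re-recruitment for drop-outs". Section 11.1 likewise replaces patients who withdraw before the procedure.

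Section 12 says the aim is not to assess efficacy in isolation "but to ascertain its acceptability to patients and physician". Section 6.2, however, lists patient acceptability as a secondary objective, and Section 6.1 makes technical feasibility the primary one.

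**The concern.** An outcome named as the objective measure of acceptability should have a formula, and this one has none. The gap seems to matter for three reasons.

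1. The questionnaire reaches only patients who had the injection. Anyone who declines by telephone, or who withdraws beforehand and is replaced, can affect the acceptability result only through the recruitment rate.
2. Entry continues until ten patients are injected. If the study completes, that count is ten by design, so the information lies in the denominator or in elapsed time, and neither is stated.
3. The visit table shows no data at the two stages where patients are identified, invited and may refuse.

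If several rates were equally defensible, the most flattering could be picked afterwards, and ten content patients might be reported without showing how many had been offered the procedure.

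**Working it through.** There is no stated figure to reproduce. Section 11.1 calls the ten patients a convenience sample, and no target rate is given. The check is whether the text leaves several real readings, and whether the data needed for the sensible one are collected.

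**1. Which event is recruitment?** Using the weeks in the visit table, with injection at week 18, against the 12-week limit in Section 8:

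- from week 0 (MDT): 18 − 0 = 18 weeks, which does not fit;
- from consent at week 5: 18 − 5 = 13 weeks, which does not fit;
- from consent at week 6: 18 − 6 = 12 weeks, which fits.

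The Visit 3 paragraph in Section 9 comes after the consent visit and repeats the 12-week interval, which also points to consent. The week-0 row is then a loose label for identification. Injection is not a third meaning. Sections 9 and 11.1 use it as the stopping count, and replacing people who drop out before the procedure presupposes that they had already been recruited.

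**2. Which denominator?** Section 7 invites those who fulfil the criteria, and Visit 1 in Section 9 has eligible patients contacted by telephone. On this wording, eligible and invited are the same group, so the rate is consented / eligible.

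**3. Are the counts available?** Section 14.2 lists a screening and eligibility checklist, drawn from the MDT and the electronic records and transferred to the eCRF. It also lists consent forms kept in the site file. The blank entries in the visit table are weak evidence that nothing is recorded: the same column omits the ultrasound and EMG reports that the Visit 3 paragraph obtains.

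**4. How far apart are the candidate rates?** The documents give no counts. Assume 20 eligible, 12 consented and 10 injected, with exact (Clopper-Pearson) 95% intervals:

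- consented / eligible = 12/20 = 60.0% (36.1 to 80.9);
- injected / consented = 10/12 = 83.3% (51.6 to 97.9);
- injected / eligible = 10/20 = 50.0% (27.2 to 72.8).

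The second is retention, which Section 9 treats separately in its withdrawal paragraph. The third is the product of the other two: 0.600 × 0.833 = 0.500. All three come from the same three counts.

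With 12 consenting, the rate is 12/15 = 80% if 15 are eligible and 12/40 = 30% (16.6 to 46.5) if 40 are. That spread reflects different data, not different definitions. It also shows that the rate does distinguish a small pool of invitees from a large one.

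**5. A rate per unit time?** Ten patients over 12 months is 10/12 = 0.83 per month. If the 42-week schedule must finish inside 52 weeks, entry lasts 52 − 42 = 10 weeks, or 10/(52/12) = 2.31 months, giving 10/2.31 = 4.33 per month. The ratio is 4.33/0.83 = 5.2. No section asks for a monthly figure, and speed of entry reflects the supply of patients as well as acceptability, so this range is not a real ambiguity in Section 6.4.2.

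**6. Participation length.** Section 7 gives 12 months. The table ends at week 42, which is 42/(52/12) = 9.7 months from identification, or 36 to 37 weeks from consent (42 − 6 and 42 − 5). This is a slip in the text and does not enter the rate.

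**The case for a change.** The strongest case for a change is that declines happen by telephone before consent, and no section explicitly lists an item for decliners or their reasons. The retention data in Section 9 start at consent. A refusal not noted at the time may be impossible to recover, and a one-line definition with a short count log would cost almost nothing. In addition, Section 7.1 includes willingness to consent among the inclusion criteria. Read literally, that would remove decliners from the eligible group and make the rate 100%.

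Part of this stands. The definition is not written down, reasons for declining are not listed, and eligible minus consented mixes refusals with patients who could not be reached.

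The rest does not carry the point. Visit 1 calls patients eligible before anyone has spoken to them, so the eligible count belongs to the stage before willingness is known, and no analyst would report the circular 100%. The number of non-consenters can be obtained from the checklist and the consent forms. Reasons for declining would be useful, but Section 6.4.2 does not promise them.

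The stakes are also modest. The Section 12 wording covers the physician as well as patients, and the physician's view is captured by the primary-endpoint questionnaire in Section 6.3. Patient acceptability also rests on seven questionnaire items, including a 0-10 score and willingness to repeat the procedure. Nor does any section say that the rate will set uptake for a later trial; Section 6.4.3 mentions sample size and follow-up rate.

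**Conclusion.** The concern does not call for a change. The recruitment rate is undefined, and Section 8 and the visit table use the word for different moments. But the text supports one natural proportion, consented over eligible, and the plan collects the counts for it. A competent analyst would report eligible, consented and injected numbers, with pre-procedure withdrawals shown, and every competing ratio can be read from those.

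On the assumed counts, the rival readings run from 50% to 83% around a natural value of 60%, whose own exact interval (36% to 81%) is wider than that range. No threshold, test or decision depends on which is quoted, and the primary objective is untouched. The week-0 label and the 12-month participation statement are clerical.

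This rests on two assumptions: that the checklist is completed and kept for every patient screened, including those who later decline, and that eligible is counted before willingness to take part is asked. If the checklist were kept only for those who consent, the denominator would be lost and the concern would regain force, but nothing in the documents says so.
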